#### 7.4.8.1. Progression-Free Survival by RECIST v1.1

Under RECIST v1.1, PFS is defined as the length of time between the baseline visit (Day 1) and the earlier of death or first assessment of PD as assessed by RECIST v1.1.

### 7.4.8.2. Progression-Free Survival by mRECIST v1.1

Under mRECIST v1.1, PFS is defined as the length of time between the baseline visit (Day 1) and the earlier of death or first overall confirmed assessment of PD (as described in Section 7.4.2.2).

### 7.4.8.2.1. Confirmation of Progression per mRECIST v1.1

Under mRECIST v1.1, the assessment of PD will be confirmed by a second consecutive assessment at least 4 weeks but no later than 6 weeks apart with the option for continuing treatment while awaiting radiologic confirmation of progression (Table 4).

• If after the first unconfirmed PD, there is an EOT/EOS or a new treatment is started, this unconfirmed PD will be counted as a confirmed PD, and DOR will be defined as the time from the first overall response (CR or PR) to this PD, or death from any cause if occurring sooner than the PD.

- If a second PD occurs after the first unconfirmed PD, the first unconfirmed PD will be counted as a confirmed PD, and DOR will be defined as the time from the first overall response (CR or PR) to the first PD, or death from any cause if occurring sooner than the confirmed PD.
- If a CR, PR, SD, or NE occurs after the first unconfirmed PD, the unconfirmed PD will not be counted as a PD. If there is no further PD assessment, DOR will be censored.

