Regular telephone conferences with study investigators will be scheduled by the sponsor in order to review cohort-specific data and overall safety data, agree on dose escalation, adjudicate individual high-grade AEs as potentially dose-limiting, and guide other major study decisions.

Efficacy Assessments:

Disease assessments will be performed based on RECIST v1.1 and also on a modified form of RECIST v1.1 (referred to as mRECIST) to account for the unique tumor response characteristics seen with immunotherapy. Modified RECIST will be defined as RECIST v1.1 with required confirmation of disease progression in the absence of clinical deterioration. The best overall response for subjects will be defined as the best overall response occurring during treatment, even if this assessment occurs after an initial assessment of progressive disease.

Assessment of tumor size (by magnetic resonance imaging or computed tomography scan) will be performed at screening or baseline (before beginning therapy) and every 8 weeks for 12 months, and then every 12 weeks thereafter until disease progression is determined. Disease progression is defined as progression confirmed by a second, consecutive assessment at least 4 weeks, but no later than 6 weeks apart with the option for continuing treatment while awaiting radiographic confirmation of progression where feasible, provided that the subject meets the following definition of clinical stability:

- Absence of clinically significant signs and symptoms (including worsening of laboratory values) indicating disease progression.
- No decline in ECOG performance status.
- Absence of rapid progression of disease.
- Absence of progressive tumors at critical anatomical sites (eg, cord compression) requiring urgent alternative medical intervention.

Subjects who discontinue study drug for a reason other than disease progression will continue to be assessed for their disease status during the follow-up phase and should continue to have tumor assessments every 8 weeks for the first 12 months and then every 12 weeks thereafter until a new cancer therapy is started, disease progression, death, or the end of the study.

Pharmacokinetic Assessments:

Serum PK samples will be obtained at Cycle 1 (Day 1, Day 2, and Day 7), Cycle 2 Day 1, Cycle 3 Day 1, Cycle 4 Day 1, Cycle 6 (Day 1, Day 2, and Day 7), and Cycle 7 Day 1. [REDACTED]

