If repeat imaging shows < 20% tumor burden compared with nadir, stable or improved previous new lesion (if identified as cause for initial disease progression), and stable/improved nontarget disease (if identified as cause for initial disease progression), then treatment may be continued or resumed. If repeat imaging confirms disease progression due to any of the scenarios listed below, subjects will be discontinued from study therapy. However, if a subject has confirmed radiographic progression (ie, 2 scans at least 4 weeks, but no later than 6 weeks apart demonstrating progression) per mRECIST, but the subject is achieving a clinically meaningful benefit, an exception to continue treatment may be considered after consultation with the medical monitor. Clinically stable subjects at the confirmatory scan should also have no further increase

in the target lesions, no unequivocal increase in nontarget lesions, and no additional new lesions develop (nonworsening disease progression) to continue study treatment (see [Section 7.7.1](#)).

In determining whether or not the tumor burden has increased or decreased, site study team should consider all target lesions as well as nontarget lesions (refer to RECIST v1.1 guidelines).

Scenarios where disease progression is confirmed at repeat imaging:

- Tumor burden remains $\geq 20\%$ and at least 5 mm absolute increase compared with nadir.
- Nontarget disease resulting in initial disease progression is worse (qualitative).
- New lesion resulting in initial disease progression is worse (qualitative).
- Additional new lesion(s) since last evaluation.

When feasible, subjects should not be discontinued until progression is confirmed. This allowance to continue treatment despite initial radiologic progression takes into account the observation that some subjects can have a transient tumor flare in the first few months after the start of immunotherapy, but with subsequent disease response. Subjects that are deemed clinically unstable are not required to have repeat imaging for confirmation of disease progression.

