### 7.4.2. Objective Response Rates and Best Overall Response

A subject is defined as an objective responder if the subject has an overall response of CR or PR at any postbaseline visit before first PD. Objective responders will be assessed based on both RECIST v1.1 and mRECIST v1.1.

Objective response rate is defined as the proportion of subjects with objective responses. Objective response rate will be estimated with 95% CIs overall by cohort-specific tumor type. Confidence intervals will be calculated based on the method for Simon 2-stage CIs of response rates outlined in Koyama and Chen (Koyama and Chen 2008). Subjects who do not have sufficient baseline or on-study response assessment information to be adequately assessed for response status will be included in the denominators in the calculation of ORR.

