## 7.4.2.1. Objective Response Rate by RECIST v1.1

Under RECIST v1.1, the best overall response is determined on subject level using the highest overall response achieved postbaseline before and including the first PD, in the order of CR, PR, SD, PD, and NE. Responses of CR, PR, or SD after the first assessment of PD will not be considered. In the case of SD, measurements must meet the SD criteria at least after the date of first dose at a minimum of 49 (56-57) days. Subjects who fail to meet this criterion will have best overall response of PD if the next available assessment indicated PD or NE if there is no additional assessment available.

For subjects with measurable disease at baseline, the RECIST v1.1 assessment criteria presented in Table 3 can be used to determine the overall disease status at a given timepoint based on the target lesion, nontarget lesion, and new lesion assessment.

Table 3: RECIST Evaluation Criteria for Overall Response: Measurable Disease at Baseline

| Target Lesions    | Nontarget Lesions | New Lesions | Overall Response |
|-------------------|-------------------|-------------|------------------|
| CR                | CR                | No          | CR               |
| CR                | Non-CR/non-PD     | No          | PR               |
| CR                | NE                | No          | PR               |
| PR                | Non-PD or NE      | No          | PR               |
| SD                | Non-PD or NE      | No          | SD               |
| Not all evaluated | Non-PD            | No          | NE               |
| PD                | Any               | Yes or No   | PD               |
| Any               | PD                | Yes or No   | PD               |
| Any               | Any               | Yes         | PD               |

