## 7.4.2.2. Objective Response Rate by mRECIST v1.1

The mRECIST v1.1 instrument was adapted from RECIST v1.1 to include criteria that accounts for new lesions that can occur in immuno-oncology subjects before the occurrence of an SD, PR, or CR. Under mRECIST v1.1, if radiologic imaging shows PD, tumor assessment should be repeated at a minimum of 4 weeks but not more than 6 weeks later to confirm the progression. If there is no second PD tumor assessment in the 4- to 6-week follow-up time, the PD will be defined as unconfirmed. Table 4 lists the scenarios that can occur after an unconfirmed PD in at least 4 weeks and no more than 6 weeks and provides rules for determining whether or not the unconfirmed PD will be counted as an event in the corresponding scenario.

Table 4: Rules for Determining PD Event Status After an Unconfirmed PD

| Event Occurring After Unconfirmed PD in the Confirmation Window (4-6 weeks) | PD Event Status   |
|---|---|
| Subject had EOS/EOT or started new anticancer therapy.                      | PD will be confirmed as a PD.   |
| Subject had a confirmed PD.   | PD will be confirmed as a PD.   |
| Subject had an CR, PR, SD, or NE.   | PD will not be considered as a PD and counted as corresponding CR, PR, SD, or NE for the second timepoint only. |

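### The SAP's mRECIST confirmation rule omits the protocol's criteria for what confirms progression, so a persisting but nonworsening new lesion can be counted as PD or as a response depending on how the repeat scan is coded

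*SAP*

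**What the plan says.** **Protocol 1.3.4.1.1.** Four findings at repeat imaging confirm progression:

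- target burden still at least 20% and 5 mm above nadir;
- worsening of the nontarget disease that caused the first PD;
- worsening of the new lesion that caused it ("New lesion resulting in initial disease progression is worse (qualitative");
- further new lesions since the last evaluation.

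The same section gives the converse: if burden is below the threshold and the causal new lesion or nontarget disease is stable or improved, treatment may go on.

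**SAP 7.4.8.2.1.** The timing rule is that "the assessment of PD will be confirmed by a second consecutive assessment at least 4 weeks but no later than 6 weeks apart". The content rule is "If a second PD occurs after the first unconfirmed PD, the first unconfirmed PD will be counted as a confirmed PD". Nothing says what must have worsened.

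**SAP 7.4.2.2 and Table 4.** The text says mRECIST has criteria that account for new lesions, but states none. The confirming row of Table 4 uses the term it should define. When the second scan is CR, PR, SD or NE, the "PD will not be considered as a PD and counted as corresponding CR, PR, SD, or NE for the second timepoint only".

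**SAP 7.4.2.1, Table 3.** This is the only timepoint-response table in the SAP: "the RECIST v1.1 assessment criteria presented in Table 3 can be used to determine the overall disease status at a given timepoint". A new lesion, or nontarget PD, gives overall PD whatever the target lesions do.

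**Where responses are cut off.** SAP 7.4.2 defines a responder, for both criteria, by "an overall response of CR or PR at any postbaseline visit before first PD". The protocol synopsis (Efficacy Assessments) takes best response on treatment, "even if this assessment occurs after an initial assessment of progressive disease". The SAP's mRECIST shells (Tables 2.2.1 and 2.2.2, footnote 2) cut at the first confirmed PD.

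**The concern.** Modified RECIST was adopted because some subjects flare before they respond. The subjects for whom it matters most are those whose first PD comes from a new lesion or nontarget disease that then stays put or shrinks. The protocol's list sets these apart from true progression. The SAP, which defines the analysed endpoint, gives a programmer no means of doing so.

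The stake is the Part 2 decision. Protocol 9.4.1.1 applies the Simon rule to the objective response rate per mRECIST: a cohort stops with 0 responders in 9 and is nonpromising with 2 or fewer in 17. At these numbers one reclassified subject turns 3/17 into 2/17. PFS under mRECIST is also affected, because an event counted this way is dated to the first PD.

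**Working it through.** **Step 1: one subject through both documents.** Suppose PD at Week 8 from a single new node. At Week 13, inside the 4-to-6-week window, the node is unchanged, target lesions are down 35%, nontarget disease is stable and there are no further lesions.

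| Source | Status of the Week 8 PD | Week 13 response |
|---|---|---|
| Protocol 1.3.4.1.1 | None of the four scenarios met, so not confirmed | Rating while the node persists is not stated |
| SAP, repeat scan rated by Table 3 with the node still entered as new | Week 13 is PD, so Week 8 is a confirmed PD | A first CR or PR here or later is not counted |
| SAP, site codes Week 13 as PR under mRECIST | Cancelled by Table 4 | PR is counted |

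The last two rows use the same images. The SAP does not say which applies.

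**Step 2: reproduce the design.** Inputs from Protocol 9.2.2 and 9.4.1.1: Stage 1 n = 9, stop at 0; 8 more for a total of 17; promising at 3 or more; rates 5% and 25%; one-sided alpha 0.05; power 80%.

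- Stage 1 stopping = (1 − p)^9.
- Power = Σ over x = 1 to 9 of Bin(9, x; p) × P(Bin(8, p) ≥ max(0, 3 − x)).

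At p = 0.25:

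- P(0) = 0.75^9 = 0.0751; P(1) = 0.2253; P(2) = 0.3003; P(≥3) = 0.3993.
- For Stage 2, P(≥2 of 8) = 0.6329 and P(≥1 of 8) = 0.8999.
- Power = 0.2253 × 0.6329 + 0.3003 × 0.8999 + 0.3993 = 0.812.

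At p = 0.05 the same sum gives alpha = 0.0466. Early stopping at 15, 20, 25, 30 and 35% is 23.2, 13.4, 7.5, 4.0 and 2.1%, matching Protocol Table 18 and SAP Table 8. The plan's figures reproduce.

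**Step 3: sensitivity to lost responses.** Let f be the share of true mRECIST responders whose first CR or PR is discarded in this way. The documents give no value, so f is an assumption. The counted rate is 0.25 × (1 − f).

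| f (assumed) | Counted ORR | Power | Stage 1 stopping |
|---|---|---|---|
| 0% | 25% | 81.2% | 7.5% |
| 5% | 23.75% | 78.1% | 8.7% |
| 10% | 22.5% | 74.5% | 10.1% |
| 20% | 20% | 66.3% | 13.4% |

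A cohort of 17 at a 25% rate expects 17 × 0.25 = 4.25 responders, so f = 10% removes 0.425 of a responder on average.

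**The case against.** **The loss is not built into the SAP.** A reader might infer that the SAP always counts nonworsening pseudoprogression as an event and discards its response. The documents do not support that. Table 3 is labelled RECIST v1.1, and nothing directs its use for mRECIST. Response is by investigator assessment, and Protocol 7.7.1 has sites apply mRECIST as the primary measure. A site that follows Protocol 1.3.4.1.1 and records SD, PR or CR is covered by Table 4 and SAP Section 9. This part of the objection stands: the outcome is undefined, not fixed.

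**The protocol is not uniform.** The synopsis describes mRECIST as RECIST v1.1 with progression confirmed at a second consecutive assessment, which is close to the SAP's rule. Sections 1.3.4.1.1 and 7.7.1 also gloss confirmed progression as two scans showing progression, and discuss nonworsening progression alongside confirmed progression. Section 7.7.1 does not repeat the four scenarios. This stands too, and it means the protocol needs work as well as the SAP. It does not supply the missing rule.

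**Other inferences that go too far.**

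- Worsening is not the only route to confirmation. Additional new lesions confirm, and target-driven PD confirms if the burden merely stays above threshold.
- The SAP does not collapse to plain RECIST. Table 4 rescues target flare that regresses and new lesions that resolve.
- A subject with CR or PR before the PD remains a responder. Because lost responders leave the DOR set, the direction of any effect on median DOR is unclear.

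**Standing of the endpoint.** Efficacy is secondary, and SAP 3.3 calls all analyses exploratory. That lowers the severity, but mRECIST ORR still decides whether cohorts continue. The SAP was written on Amendment 2, but SAP 2.1 keeps it in force for later amendments.

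**Conclusion.** The point holds as a gap in the endpoint definition and should be fixed. For PD caused by a new lesion or nontarget disease, Protocol 1.3.4.1.1 does not accept persistence without worsening as confirmation, unless there are additional new lesions or the target burden is still above threshold. The SAP confirms by a second PD in the window without those criteria and has no mRECIST timepoint table. Coding practice would then decide whether such a subject is a responder or a progression. Separately, SAP 7.4.2 cuts responses at the first PD under both criteria, which conflicts with the synopsis and with the SAP's own mRECIST shells.

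The size is unknown. The figures of 78.1% to 66.3% for power and 8.7% to 13.4% for Stage 1 stopping rest entirely on the assumed 5% to 20% loss at a true rate of 25%. If sites code these scans under mRECIST, the loss could be close to zero. Within that assumption, even 5% takes power just below the stated 80%.

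**What to change.** 1. In SAP 7.4.2.2, Table 4 and 7.4.8.2.1, define confirmation as a repeat scan in the 4-to-6-week window that meets at least one of the four scenarios in Protocol 1.3.4.1.1.
2. Add an mRECIST timepoint-response table consistent with those scenarios. The sponsor must state how overall response is rated while a nonworsening new lesion persists, since neither document says.
3. In SAP 7.4.2, cut responses at first confirmed PD for mRECIST and keep first PD for RECIST v1.1.
4. Reconcile the two-scan wording in the protocol synopsis and in Sections 1.3.4.1.1 and 7.7.1 with the four scenarios, so that both documents use one definition of confirmed progression.

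The cost is SAP text, derivation code and a protocol clarification. Target, nontarget and new-lesion assessments are already planned for listing (Listings 2.5.3 to 2.5.5). The sponsor should check that the CRF captures the qualitative judgement of worsening, which the documents do not show. The rule should be settled before Stage 1 responses are read.

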## 7.4.8. Progression-Free Survival

Progression-free survival is defined as the length of time between the baseline visit (Day 1) and the earlier of death or PD as assessed by RECIST v1.1 and mRECIST v1.1. Date of death will be determined using the Death Report CRF.

Censoring for PFS will follow the algorithm outlined in Table 5, which is based on the FDA Guidance for Industry: Clinical Trial Endpoints for the Approval of Cancer Drugs and Biologics (FDA 2007).

Kaplan-Meier curves for PFS will be presented by cohort-specific tumor types. The KM estimate of median PFS will be presented with its 95% CI. The 95% CI will be calculated using the Brookmeyer and Crowley's method (Brookmeyer and Crowley 1982).

Table 5: Evaluation and Censoring of Progression-Free Survival

| Situation   | Outcome    | Date of Progression or Censoring   |
|---|------------|--|
| No baseline tumor assessments                                 | Censored   | Date of Day 1  |
| No valid postbaseline response assessments                    | Censored   | Date of Day 1  |
| Progression documented between scheduled response assessments | Progressed | Date of first overall response of PD   |
| No progression  | Censored   | Date of last valid radiologic assessment (not NE and not missing)  |
| Study discontinuation for undocumented progression            | Censored   | Date of last valid radiologic assessment (not NE and not missing)  |
| Study discontinuation for toxicity or other reason            | Censored   | Date of last valid radiologic assessment (not NE and not missing)  |
| New anticancer treatment started                              | Censored   | Date of last valid radiologic assessment (not NE and not missing) on/before starting a new anticancer treatment. (Date of PD assessment if the new anticancer treatment started after PD.) |
| Death before first progressive response assessment            | Progressed | Date of death  |
| Death between adequate response assessments                   | Progressed | Date of death  |
| Death or progression after more than 1 missed assessments     | Censored   | Date of last valid radiologic assessment (not NE and not missing) before death   |

NE = not evaluable.

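### The SAP's mRECIST rules both count and cancel an unconfirmed PD followed by a not-evaluable scan and then end of treatment, and SAP Table 5 does not carry the protocol's radiation rule for PFS

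*SAP*

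**What the plan says.** **Unconfirmed PD.** SAP 7.4.8.2.1 opens by requiring that "the assessment of PD will be confirmed by a second consecutive assessment at least 4 weeks but no later than 6 weeks apart". Its first bullet then reads: "If after the first unconfirmed PD, there is an EOT/EOS or a new treatment is started, this unconfirmed PD will be counted" as confirmed. Its third bullet reads: "If a CR, PR, SD, or NE occurs after the first unconfirmed PD, the unconfirmed PD will not be counted as a PD", and continues: "If there is no further PD assessment, DOR will be censored". SAP Table 4 (Section 7.4.2.2) holds the same pair of rules, limited to events in the 4-6 week confirmation window. Its first row ("Subject had EOS/EOT or started new anticancer therapy") confirms the PD. Its third row, for CR, PR, SD or NE, says "PD will not be considered as a PD and counted as corresponding CR, PR, SD, or NE for the second timepoint only". Footnote [1] of shell Tables 2.2.1 and 2.2.2 repeats both rules. The bullets and footnotes do not carry Table 4's window, and no place says which rule wins when both events occur.

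These rules feed mRECIST PFS (7.4.8.2), mRECIST DOR (7.4.4.2) and duration of disease control (7.4.5). RECIST v1.1 PFS and DOR use the first PD and do not depend on them.

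**Palliative radiation.** Protocol 5.6.3 allows it only exceptionally and treats it as clinical progression for PFS. Protocol 2.2.2 and SAP 7.4.8 define PFS by assessed progression or death. SAP Table 5 has no radiation row. Its nearest rows, new anticancer treatment and discontinuation for undocumented progression, both censor. SAP 7.4.4 gives DOR the PFS censoring algorithm.

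**The concern.** An NE scan neither confirms nor refutes a progression, yet the SAP gives it the same cancelling power as a scan showing stable disease or response. A subject who progresses, has one unreadable repeat scan and then stops treatment satisfies one instruction to count the event and another to drop it. Two programmers can follow the SAP faithfully and give that subject different event status. The NE rule also works in one direction only: it can delay or remove mRECIST events, never add or advance one.

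For radiation, the protocol's statement and the SAP's table lead to different outcomes for the same subject. Whether radiation is a new anticancer treatment is also open. Protocol 3.2, criterion 3, lists radiation within the washout for anticancer medication, while Protocol 5.6.3 lists the two separately. Part 2 cohorts hold at most 17 evaluable subjects, so a single subject is visible in a Kaplan-Meier curve.

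**Working it through.** The plan states no figure for this point, so there is none to reproduce. The check has three parts.

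**1. Apply the rules as written.** Weeks are counted from the PD scan.

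| Sequence after the PD | Bullets and shell footnotes (no window) | Table 4 (weeks 4-6) |
|---|---|---|
| EOT at 5 | counted | counted |
| NE at 5 | cancelled | cancelled |
| NE at 4, EOT at 5 | counted and cancelled | counted and cancelled |
| NE at 5, new therapy at 6 | counted and cancelled | counted and cancelled |
| NE at 5, EOT at 8 | counted and cancelled | cancelled |
| NE at 3, EOT at 5 | counted and cancelled | counted |
| SD at 5, EOT at 20 | counted and cancelled | cancelled |

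Rows 3 and 4 conflict wherever one looks. Rows 5 to 7 show the missing window making the bullets disagree with Table 4. The last row shows that the precedence gap is not confined to NE. SAP Table 5 does not settle the matter. Its entry for new therapy after PD, "Date of PD assessment if the new anticancer treatment started after PD", presupposes that the PD still stands.

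**2. Size of (a).** The documents give no NE frequency, so every input below is an assumption.

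*One subject.* Take 17 subjects with 5, 4 and 2 PDs at weeks 8, 16 and 24, and six later. Kaplan-Meier PFS at week 26 is 12/17 × 8/12 × 6/8 = 6/17 = 35.3%. Change one PD from event to censored. The SAP does not say whether a cancelled PD scan is itself a valid assessment, so two censoring dates are shown.

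| PD at week | Censored at previous scan | Censored at PD scan |
|---|---|---|
| 8 | 12/16 × 8/12 × 6/8 = 37.5% (+2.2 points) | 13/17 × 8/12 × 6/8 = 38.2% (+2.9) |
| 16 | 12/17 × 8/11 × 6/8 = 38.5% (+3.2) | 12/17 × 9/12 × 6/8 = 39.7% (+4.4) |
| 24 | 12/17 × 8/12 × 6/7 = 40.3% (+5.0) | 12/17 × 8/12 × 7/8 = 41.2% (+5.9) |

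*On average.* Assume median PFS of 16 weeks and 8-weekly scans. Then r = 2^(-8/16) = 0.7071 per scan, h = 1 - r = 0.2929, and week-26 PFS is r³ = 35.4%. Let p be the share of PDs that follow the disputed sequence.

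- Censored at previous scan: [1 - h(1-p)/(1-hp)]³.
- Censored at PD scan: [1 - h(1-p)]³.
- Chance of at least one case among 17 progressing subjects: 1 - (1-p)^17.

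| p | Rise, previous scan | Rise, PD scan | At least one of 17 |
|---|---|---|---|
| 0.5% | 0.2 points | 0.2 points | 8% |
| 1% | 0.3 | 0.4 | 16% |
| 2.5% | 0.8 | 1.1 | 35% |
| 5% | 1.6 | 2.2 | 58% |

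**3. Size of (b).** Use the same 17 subjects with one irradiated. The three handlings are event at radiation, ignored, and censored at the last prior scan.

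- Radiation at week 4, PD at week 8. Event or ignored gives 6/17 = 35.3%. Censored gives 6/16 = 37.5%. The spread is 2.2 points.
- Radiation at week 20, PD at week 32. Event gives 5/17 = 29.4%. Ignored gives 6/17 = 35.3%. Censored gives 8/17 × 5/7 = 33.6%. The spread is 5.9 points.

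**The case against.** The strongest reply is that the next event after the PD decides. Table 4's column heading speaks of a single event, and the lead-in to 7.4.8.2.1 speaks of the next consecutive assessment. Every subject eventually reaches end of treatment, so a cumulative reading would revive even PDs refuted by SD, PR or CR, which cannot be intended. This is a sensible reading, but the SAP does not state it. It also leaves the substantive problem in place, because the NE would then erase a PD that end of treatment alone would have confirmed.

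A second reply is that the NE rule is prespecified, appears consistently in Table 4, the bullets and both footnotes, and fits the protocol's requirement of confirmation at 4-6 weeks. What stands is that holding a PD open through an NE until some later scan would go beyond the protocol's window, so that is not asked for here. PD, NE, PD is also less clear-cut: the lead-in and Protocol 7.7.1 can be read to date the event at the later PD. Two supports are weaker than they look. Protocol Table 12 names only SD, PR and CR as non-confirming results, but it governs imaging and treatment and is silent on NE. SAP Table 5 excludes NE only when choosing a censoring date.

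Third, the effect is small against sampling error. The standard error of 6/17 is √(0.353 × 0.647/17) = 11.6 points. That is correct.

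On radiation, a reader might infer that the documents contain no rule at all, or that radiation must also end DOR. They do not support either. Protocol 5.6.3 gives one explicit rule for PFS. It says nothing on DOR, and SAP 7.4.4 imports only PFS censoring, not PFS events.

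**Conclusion.** Both parts hold as gaps in the analysis rules, and both should be corrected before database lock. For (a), PD followed by NE and then EOT/EOS or new therapy within the window is both counted and cancelled. If the NE governs, an uninformative scan removes an mRECIST event. For (b), the SAP's PFS definition and Table 5 do not carry the protocol's statement on palliative radiation.

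The size is unknown. One reclassified subject is worth about 2 to 6 points of week-26 PFS in the assumed cohort of 17. The average effect of the disputed sequence is 0.2 to 2.2 points if it makes up 0.5% to 5% of PDs.

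A reader might infer that the response-rate decision is at risk. For PD, NE, EOT with no later scan, best overall response can differ only between PD and NE. Neither is a response, and SAP 7.4.2 keeps unassessable subjects in the denominator. The Simon rule, sample size and power do not change. RECIST v1.1 PFS and DOR, reported alongside, are untouched by (a). SAP 3.3 calls all the analyses exploratory.

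**What to change.** **(a)**
- Remove NE from Table 4 row 3, from the third bullet of 7.4.8.2.1, and from footnote [1] of shells 2.2.1 and 2.2.2, so that only CR, PR or SD cancels an unconfirmed PD.
- State that EOT/EOS or new therapy after an unconfirmed PD, with no intervening CR, PR or SD, is an event dated at the first PD.
- State that a PD already refuted by CR, PR or SD is not revived by a later EOT/EOS.
- Put Table 4's window into the bullets and footnotes, and say what applies when only an NE falls inside it.
- Reconcile the PD, NE, PD date with Protocol 7.7.1. A sensitivity analysis with the other date is optional.

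**(b)** Reconcile Protocol 2.2.2 and 5.6.3 with SAP Table 5. Add one radiation row with a stated outcome and date for PFS under both criteria. Say whether radiation is a new anticancer treatment and how DOR handles it.

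The cost is a few SAP lines, one table row, two shell footnotes and minor programming. Reported mRECIST PFS and DOR may become slightly shorter.
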